Official Title: Follicle Activation in Patients with Poor Ovarian Response Through Fragmentation of the Ovarian Tissue.

ClinicalTrials.gov.ID: NCT02354963

Document date: 10th April 2022

Study Protocol

List of contents

1. Scientific background	1
2. Hypothesis.....	3
3. Objectives.....	3
4. Study design	3
5. Methods.....	5
6. References.....	6

1. Scientific background

Assisted reproductive techniques (ART) are increasingly used to treat infertility. In vitro fertilization (IVF) involves pharmacological stimulation of the ovary in a supra-physiological manner with gonadotrophins to obtain multiple follicles. However, many women do not respond adequately to the usual treatment protocols during controlled ovarian hyperstimulation. These patients have been classified as "low responders" and have lower gestation rates compared to "normoresponders", ranging from 0 to 18% (Tarlatzis et al., 2003). The incidence of low ovarian response in IVF treatments is estimated to be around 10-25% (Pellicer et al., 1998). The wide range of prevalence described in the literature is explained by the lack of consensus on the specific clinical criteria that have been used to define low response. Given the disparity of criteria, the ESHRE (European Society of Human Reproduction and Embryology) established a consensus definition for low response:

- Option 1: two episodes of poor ovarian response (≤ 3 oocytes retrieved on a conventional schedule) in the absence of advanced maternal age or evidence of low ovarian reserve.
- Option 2 at least two of the following: age ≥ 40 years or any other risk factor for poor ovarian response, previous IVF cycle with ≤ 3 oocytes (following a conventional stimulation protocol), abnormal ovarian reserve test (antral follicle count of ≤ 5 , AMH $< 0.5 - 1.1$ ng/mL).

Pathophysiological basis of low response

- Ovarian reserve: the concept of low responder is closely related to that of ovarian reserve. Ovarian reserve is defined as the number and degree of quality of follicles remaining in the ovary at a given time (Broeckmans et al., 2006) and is the main determinant of ovarian response to gonadotrophin stimulation (Pellicer et al., 1998).
- Other causes: a group of young women with low ovarian response have normal basal FSH hormone levels in whom there is no apparent cause for this response (Tarlatzis et al., 2003). Many hypotheses have been proposed to explain this condition. However, none have been proven: a decrease in the number of FSH receptors available in the granulosa cells, FSH post-receptor defects, etc.

Strategies aimed at improving the management of responding casualties

Efforts to provide better control of responding casualties have currently focused on a priori identification of responding casualties and modification of existing protocols themselves.

A priori identification of responder casualties

- Antral follicle count by transvaginal ultrasound: Antral follicle count is nowadays considered the best predictor of ovarian response in isolation (Broeckmans et al., 2006). Most authors use as a cut-off point 3-4 antral follicles on the day when pituitary suppression is proven.
- FSH elevation at the beginning of the cycle: In disuse because of its variable sensitivity and specificity.
- Maternal age: The probability of not conceiving the first child within one year increases from 5% in women in the 20-30 age group to 30% in women over 35 (Broeckmans et al., 2006).
- Anti-Müllerian hormone (AMH): recently, it has been proposed that the determination of AMH) in blood could be used as a test of ovarian reserve so that decreased levels would indicate ovarian aging. Its efficacy is similar to that of the antral follicle count (Broeckmans et al., 2006).

Therapeutic modifications aimed at reducing the incidence of low response

Since the beginning of ART application, many different protocols have been proposed to manage patients with low response, obtaining very different results in the further studies published, making it very difficult to conclude them. Increasing the dose of FSH used (Tarlaltzis et al., 2003), the use of recombinant FSH instead of purified urinary FSH (Raga et al., 1999), the use of FSH in the luteal phase (Rombauts et al., 1998), modifications in pituitary desensitization protocols (García-Velasco et al. 2000), or pre-treatment with estrogens or combined oral contraceptives (Fanchin et al., 2005), pre-treatment with androgens (Fábregues et al., 2009). The reality is that none of these interventions have been shown to be effective in increasing the gestation rate in the subgroup of low responders.

New strategy for ovulation stimulation

In every woman, even in the low responder, there is a pool of dormant (primordial) follicles, not stimulable with gonadotrophins, which, if they could be used would significantly increase the functional reserve of the patient. Aaron Hsueh's research group described a follicular activation technique (Kawamura et al., 2013), which consists of activating these primordial follicles and converting them into antral (stimulable) follicles before the IVF cycle is performed by fragmenting the ovarian tissue. Fragmentation of the ovarian cortex increases actin polymerization and disrupts the intracellular Salvador/Warts/Hippo (SWH) signaling pathway. The SWH pathway is responsible for maintaining proper organ size. Its disruption leads to increased cell growth and survival because CCN (growth factors) and BIRC (inhibitors of apoptosis) levels are increased, resulting in activation of primordial follicles. This explains why the final consequence of ovarian fragmentation is the growth of ovarian primordial follicles and

therefore the generation of a greater number of antral follicles, which are susceptible to stimulation with gonadotrophins, thus potentially increasing the number of mature oocytes that could be obtained in patients undergoing the technique.

From a practical point of view, by laparoscopic surgery, the ovarian cortex is removed, mechanically stimulated in vitro (the cortex is fragmented into multiple aliquots), and then reimplanted, and the conventional IVF cycle is carried out.

This technique was tested in 27 patients with primary ovarian failure (early menopause, the paradigm of ovarian unresponsiveness). The results were as follows: eight patients presented follicular growth, obtaining mature oocytes from five of them and achieving pregnancy in one patient who finally gave birth to a healthy baby. It should be noted that this study was carried out in a "worst-case scenario", in menopausal patients of whom only thirteen had residual follicles in the histological analysis of the pieces, and the eight in whom ovulation was induced belonged to this group, which represents a 62% response to treatment.

2. Hypothesis

The fragmentation of the ovarian cortex in vitro activates the growth of primordial follicles, leading to the appearance of a greater number of antral follicles, which would make it possible to obtain more oocytes after controlled ovarian stimulation in patients with low ovarian response, which would be useful for improving the success rate of IVF in patients with low ovarian response.

3. Objectives

Main objective:

- To assess whether the fragmentation of ovarian cortex increases the pool of antral (potentially stimulable) follicles.

Secondary objectives:

- To analyse whether the proposed intervention improves ovarian response after gonadotrophin stimulation.
- To evaluate the pregnancy rate.

4. Study design

TYPE OF STUDY

Two-phase study:

- Phase 1: Randomised, controlled, single-blinded clinical trial. Sixty patients previously confirmed as low responders according to ESHRE criteria will be randomised to two treatment arms after assessment of ovarian reserve:

- Arm 1 (control): no intervention was performed on the patient.
- Arm 2 (intervention): removal of ovarian cortex by unilateral laparoscopic oophorectomy, fragmentation of ovarian tissue into 2 mm² aliquots. The ovarian tissue was then re-transplanted under the serosa of the tube homolateral to where the cortex was removed.

Subsequently, bi-weekly ultrasound monitoring was performed to determine the number of antral follicles present in both the native ovary and the re-implanted ovary to determine the number of antral follicles. The number of antral follicles in both intervention groups was compared and the number of antral follicles in the native ovary was also compared with the reimplanted one in each of the patients.

- Phase 2 Prospective observational study. A cohort of all patients who participated in phase 1 was formed and followed for six months. Those patients who wished to undergo IVF treatment received standard treatment for low responders. The final objective consisted of assessing the gestation rate in both groups, as well as the parameters related to the reproductive technique.

STUDY POPULATION

Patients affected by infertility requiring treatment by IVF or ICSI and who were confirmed low responders based on the inclusion criteria.

INCLUSION CRITERIA (one must be met)

- At least two episodes of poor ovarian response (≤ 3 oocytes retrieved in a conventional scheme).
- A previous IVF cycle with ≤ 3 oocytes (following a conventional stimulation protocol) and presence of an abnormal ovarian reserve test (antral follicle count of ≤ 5 or AMH ≤ 5 pM).

EXCLUSION CRITERIA (the presence of one excludes from participation)

- Patients older than 40 years.
- Clinical suspicion of endometriosis.

- Anovulatory patient (defined by the presence of irregular cycles and serum progesterone on day 21 of the cycle of ≤ 10 ng/mL).
- Couples with severe male factor: severe oligoasthenozoospermia, oligoasthenoteratozoospermia and azoospermia.
- All patients who do not voluntarily give their express written consent.

STUDY VARIABLES

PHASE 1

- Antral follicle count at randomisation (per ovary).
- Antral follicle count after intervention/control (per ovary, fortnightly for 6 months).
- Determination of AMH and FSH/E₂ at the time of randomisation.
- AMH, FSH/E₂ determination after intervention/control (per ovary, monthly for 6 months).

PHASE 2

- Number of metaphase II oocytes obtained after ovarian stimulation.
- Number of follicles punctured.
- Total number of oocytes obtained after ovarian stimulation.
- Number of fertilised oocytes.
- Evolution of embryo development.
- Serum oestradiol levels on the day of hCG.
- Total dose of FSH used.
- Necessary days of gonadotrophin stimulation.
- Clinical pregnancies (determined as the presence of the sac after embryo transfer).
- Progressive gestations (those exceeding 12 weeks).

5. Methods

ASSESSMENT OF OVARIAN RESERVE

- Basal and follicular serum determination of steroid hormones: serum determinations of FSH, E₂ and AMH) were performed with a microparticle immunoassay kit integrated into the ABBOTT AxSYM® Plus system and 5.20 software (Abbott Laboratories, Abbot Park, IL, USA).

- Ultrasound determinations: antral follicle counting was performed with a GE iVoluson (General Electric, Spain) equipped with 3D vaginal transducer (6.5-9MHz). Antral follicles were counted on day 2-5 of the menstrual cycle.

REMOVAL AND REIMPLANTATION OF THE CORTEX

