Official Title: Follicle Activation in Patients with Poor Ovarian Response Through Fragmentation of the Ovarian Tissue.

ClinicalTrials.gov.ID: NCT02354963

Document date: 10th April 2022

Statistical Analysis Plan

Statistical Analysis Plan

The allocation of patients to the study groups was performed using a random number generator (www.random.org), the numbers generated were included in a sealed envelope that was opened at the time of patient randomization.

Information on study variables was collected in a data record booklet (DRB) designed specifically for this study. A database was created to contain the information from the CRFs of the included patients and was equipped with internal consistency rules to control for inconsistencies and/or inaccuracies in data collection and tabulation. The internal coherence rules were guaranteed based on index fields that avoid duplicate records, detect out-of-range or suspicious data and prevent the recording of unrelated data. Before the computerization of the data, a thorough review of the data CRFs was carried out to ensure maximum reliability of the record.

Statistical analysis was performed with the SPSS 2.0.0 statistical package. Variables that followed a normal distribution were expressed as mean and standard deviation, and variables that did not follow a normal distribution were described as median and range. Categorical variables were expressed as absolute values and percentages. Observed differences were considered statistically significant if $p < 0.05$. Comparison of quantitative variables was performed using the Student's t-test or U-Mann test, as appropriate. Comparison of categorical variables was performed using the Chi-square or Fisher test, as appropriate.

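### The SAP names no paired test for non-normal native-versus-reimplanted ovary counts; its only option there, Mann-Whitney U, is miscalibrated if a woman's two ovaries are correlated

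*Protocol*

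**What the plan says.** Protocol section 4 (Type of study, Phase 1) plans two comparisons of antral follicle count. One is between arms: "The number of antral follicles in both intervention groups was compared". The other is within women: "the number of antral follicles in the native ovary was also compared with the reimplanted one in each of the patients". Only Arm 2 women have a reimplanted ovary, so the second contrast belongs to that arm alone.

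Counts are repeated: "bi-weekly ultrasound monitoring was performed to determine the number of antral follicles present in both the native ovary and the re-implanted ovary". Section 4 (Study variables, Phase 1) lists them for each ovary at randomisation and then every two weeks for six months. Section 5 (Assessment of ovarian reserve) adds: "Antral follicles were counted on day 2-5 of the menstrual cycle".

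The SAP's third paragraph covers all quantitative comparisons by Student's "t-test or U-Mann test, as appropriate". It expects some non-normal data: "variables that did not follow a normal distribution were described as median and range". It does not mention the within-woman contrast or say what is checked for normality. Neither document names a signed-rank test, a mixed model or any other paired method.

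**The concern.** Mann-Whitney U assumes two independent groups. Two ovaries in one woman share her age, hormonal state and reserve, so independence cannot be taken for granted. The non-normal branch is also a real prospect: per-ovary counts are small integers, in women for whom a count of 5 or less is one route into the trial.

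At stake is the reliability of the p-value for the contrast that shows most directly where new follicles appear. Only about 30 women can inform it (60/2, if allocation is 1:1; the ratio is not stated).

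**Working it through.** **Inputs.** From the documents: 60 women in two arms, significance at p < 0.05, counts per ovary. Assumed, because the documents are silent: 30 pairs, two-sided testing, inter-ovary correlation r, mean 2.5 per ovary (a total of 5, halved) and the effect size. The plan has no power figure to reproduce.

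**1. Which branch fails.** If the data are judged normal, Student's test can be taken in its paired form and nothing is lost. If they are judged non-normal, the only listed test is Mann-Whitney. The words leaving the choice to what is appropriate can select among listed tests but cannot supply one that is not listed.

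**2. Size, normal approximation.** An unpaired test takes the variance of the mean difference as 2σ²/n; with pairs it is 2σ²(1−r)/n. The true size at nominal 5% is therefore 2[1 − Φ(1.96/√(1−r))]:
- r = 0.3: 1.96/0.837 = 2.34, size 1.9%
- r = 0.5: 1.96/0.707 = 2.77, size 0.6%
- r = −0.3: 1.96/1.140 = 1.72, size 8.6%

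**3. Size and power, simulated Poisson counts** (30 pairs, mean 2.5; power is for a uniform 50% increase, 2.5 against 3.75):

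| r | Mann-Whitney true alpha | Mann-Whitney power | Signed-rank power |
|---|---|---|---|
| 0 | 5.0% | 74% | 74% |
| 0.3 | 2.0% | 79% | 88% |
| 0.5 | 0.7% | 81% | 96% |
| 0.7 | 0.1% | 87% | 99.7% |

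Signed-rank alpha stayed at 4.6–5.4%. A separate run at r = 0.5 gave alpha of about 0.5% and power of 82% against 97%. At r = −0.3, simulated Mann-Whitney alpha was 8–9%.

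Sensitivity at r = 0.5, Mann-Whitney against signed-rank:
- Mean 1.5: 53% against 83%.
- Mean 4: 97% against 99.7%.
- Overdispersed counts (negative binomial, size 2.5), mean 2.5: 35% against 68%.
- A doubling of Poisson counts: both above 99%.

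**4. How often the failing branch is reached.** The SAP names no normality test; Shapiro-Wilk at 5% is assumed. With no true difference, checking each ovary's raw counts declares non-normality in 88–100% of samples. Checking the within-woman difference does so in 18/28/44/79% at r = 0/0.3/0.5/0.7 (Poisson). So what is checked largely decides whether the pairing survives.

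**5. Baseline.** Pairing does not remove a side difference that predates surgery. The check used a normal model with SD 1.58, inter-ovary correlation 0.3, baseline/follow-up correlation 0.3–0.6 and no treatment effect.
- Stable side difference of 0.5 or 1.0 follicles: a follow-up-only paired test rejects in 29% or 80%; change from baseline rejects in 5%.
- Operated side picked as the one with the higher baseline count: change from baseline rejects in 53–81%; adjusting for the baseline difference rejects in 5%.

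This supports the baseline part of the fix, not the severity.

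**6. A mixed model is not automatically safe.** Suppose only a woman-level random effect is fitted over m visits, with inter-ovary correlation 0.3 and same-ovary between-visit correlation 0.5. For m = 6:
- The average within-woman correlation is (5×0.5 + 6×0.3)/11 = 0.391, so the model takes the variance of a woman's mean difference as 2(1−0.391)/6 = 0.203.
- The true variance is 2[(1 + 5×0.5)/6 − 0.3] = 0.567.
- The ratio is 2.79, its root 1.67, and 1.96/1.67 = 1.17, which gives about 24% false positives.

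Simulation over same-ovary correlations of 0.5–0.8 gave 24–47% with 6 visits and 38–61% with 13. A paired test on each woman's mean difference gave about 5%.

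**The case against.** The strongest reply is that the protocol already frames the contrast within each patient, and that an analyst free to choose the appropriate Student's test would pair it. That stands. A reader might infer that the SAP prescribes an unpaired test here; it does not, and the defect is confined to the non-normal branch.

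Second, a reader might infer that the only possible error is lost power. That holds only for non-negative correlation. The documents do not give its sign, least of all after one ovary has been removed, fragmented and grafted, and a negative value makes Mann-Whitney anti-conservative.

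Third, a reader might infer that signed-rank is always the more powerful choice. That rests on a uniform shift. Protocol section 1 reports follicular growth in 8 of 27 women (30%), or 8 of the 13 with residual follicles (62%), in a different population, so all-or-none grafts are plausible. In simulations with 30% or 62% of grafts active, Mann-Whitney generally rejected more often than signed-rank, for example 96% against 75% and 60% against 52%. The case for pairing is therefore calibration first; the power gain is conditional.

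Fourth, every size quoted rests on assumed inputs. That is so, and the figures are illustrations. The structural point, that no paired method is listed for non-normal data, does not depend on them.

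**Conclusion.** The concern holds in limited form, as a minor point. If the native and reimplanted counts are judged non-normal and the SAP is followed as written, the test used assumes an independence that the design does not provide. Under 30 pairs and a Poisson mean of 2.5, true alpha is about 2% at r = 0.3, 0.5–0.7% at r = 0.5 and about 9% at r = −0.3. For a uniform 50% increase at r = 0.5, power is 81–82% rather than 96–97%. At zero correlation, or with a paired t-test, nothing is lost.

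A reader might also infer that the trial's main comparison is compromised. The documents do not support that: the within-woman contrast is introduced as an additional comparison, and the named tests suit the between-arm comparison provided that it uses one value per woman.

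**What to change.** State in the SAP that, in Arm 2, the native-versus-reimplanted contrast analyses the within-woman difference by paired t-test, or by Wilcoxon signed-rank test if that difference (not the raw counts) is non-normal. Apply it at one named visit or to one per-ovary summary over the visits.

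Use the per-ovary count already recorded at randomisation, because randomising women does not balance operated and native sides. Make change from baseline the main form, with adjustment for the baseline difference as a sensitivity analysis, and report how the operated side was determined.

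If a mixed count model is preferred, it must include an ovary-within-woman random effect, allowing the side difference to vary between women. A woman-level effect alone is not enough.

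The cost is a short SAP paragraph, with no new data, procedures or patients. The downsides are that one visit or summary must be chosen, that change scores add noise when baseline and follow-up counts are weakly correlated, and that neither baseline method suits every way the side could have been chosen. Both documents are written largely in the past tense, so if the data have already been analysed, the SAP should record which test was used and any re-analysis should be labelled post hoc.

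### Women with normal and with reduced ovarian reserve can both enter, but neither allocation nor the planned comparison of antral follicle counts uses the baseline reserve already measured, which costs precision in 60 women.

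*Protocol*

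**What the plan says.** **Entry.** Protocol section 4 makes the criteria alternatives: "INCLUSION CRITERIA (one must be met"). Route 1 is "At least two episodes of poor ovarian response (≤ 3 oocytes retrieved in a conventional scheme"), with no reserve test. Route 2 is one earlier cycle with at most 3 oocytes plus "presence of an abnormal ovarian reserve test (antral follicle count of ≤ 5 or AMH ≤ 5 pM").

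Protocol section 1 restates the ESHRE definition, whose two-episode option applies "in the absence of advanced maternal age or evidence of low ovarian reserve". The trial's first criterion drops the reserve part of that condition, so route 1 can hold women with normal reserve and women with reduced reserve.

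**Role of reserve.** Protocol section 1 says that ovarian reserve "is the main determinant of ovarian response to gonadotrophin stimulation". The main objective in section 3 is the pool of antral follicles, and AFC is itself one of the entry tests.

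**Data available.** Section 4 places randomisation after the assessment of reserve. Its study variables include AFC per ovary, AMH and FSH/E2 at randomisation, and AFC per ovary every two weeks for six months afterwards.

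**Allocation and analysis.** The SAP states: "The allocation of patients to the study groups was performed using a random number generator", with the numbers held in sealed envelopes. It mentions no stratification or blocking. Quantitative variables are compared by Student's t-test or the Mann-Whitney test, with no covariate, stratum or baseline value.

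**The concern.** The main outcome is a follicle count, and some women qualify because that same count was 5 or less before treatment. Others may qualify with a higher count. The count at entry is therefore likely to explain a good part of the count at follow-up, whatever the treatment does.

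An unadjusted comparison leaves all of that variation in the error term. In a trial of 60, the arms may also differ by chance in their mix of reserve. The planned test would then give no way to tell how much of an observed difference, or of its absence, came from that mix. The data needed to deal with this are already collected, but the plan does not use them.

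**Working it through.** **Inputs from the documents.** 60 women in two arms; significance at p < 0.05. No effect size, SD, power or dropout is given, so the 60 cannot be reproduced.

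**Assumptions, not in the documents.** 30 per arm; two-sided test; share p of women with normal reserve 20 to 50%; gap D in AFC between normal- and reduced-reserve women 2 to 6 follicles; within-group SD s = 3 follicles (s = 2 where stated).

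**1. Chance imbalance.** With K normal-reserve women among 60 and a fixed 30/30 split, the number X in one arm is hypergeometric, and the shares differ by |2X − K|/30. A gap of at least 20 points means |2X − K| ≥ 6.

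- p = 30% (K = 18), X ≤ 6 or X ≥ 12: probability 15.8%.
- p = 50% (K = 30), X ≤ 12 or X ≥ 18: probability 19.6%.

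The SAP does not say that arm sizes were fixed. Under simple allocation (each woman independently, probability one half) the exact figures are 10.0% and 15.5%. They are lower partly because a gap of exactly 20 points is a common outcome with a 30/30 split and is counted here.

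**2. Effect on the arm difference.** Shift = imbalance × D: 0.20 × 3 = 0.6 and 0.20 × 4 = 0.8 follicle.

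**3. Power lost without adjustment.** The benchmark is the effect with 80% power when reserve group is adjusted for: (1.96 + 0.84) × √(2/30) = 0.723 SD, and 0.723 × 3 = 2.17 follicles. Without adjustment, the SD is √(s² + p(1 − p)D²) and power = Φ(2.17/(SD × √(2/30)) − 1.96). At D = 4:

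| p | SD | SE of difference | Power |
|---|---|---|---|
| 20% | √(9 + 0.16 × 16) = 3.40 | 0.878 | 70% |
| 30% | √(9 + 0.21 × 16) = 3.52 | 0.908 | 67% |
| 50% | √(9 + 0.25 × 16) = 3.61 | 0.931 | 64.5% |

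Over the same range of p, power is 76 to 77% at D = 2 and 51 to 59% at D = 6. To restore 80% at D = 4 without adjustment takes 39 to 44 women per arm, against 31 adjusted (30 rounded up).

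**4. Check by simulation** (6,000 trials per setting, D = 4, 30 per arm). With no treatment effect, the unadjusted t-test rejects in 4.5% (p = 30%) and 5.1% (p = 50%), so type I error is not inflated. With an effect of 2.17, power is 65% unadjusted and 77% adjusted at p = 30%, and 63% and 78% at p = 50%. These are slightly below the table because the tests use the t distribution.

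**5. Adjusting for baseline AFC itself.** If 3 is the SD of the follow-up count and its correlation with baseline is r, the residual SD is 3√(1 − r²): 2.60 at r = 0.5 and 2.14 at r = 0.7 (assumed values). Power for 2.17 follicles rises from 80% to 90% and 98%.

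**The case against.** **It is precision, not bias.** Randomisation makes the unadjusted estimate unbiased on average, and its standard error already allows for chance imbalance. A shift of 0.6 to 0.8 follicle is about one standard error or less: at p = 50% the SE is 0.87 to 0.93 with s = 3, and 0.65 to 0.73 with s = 2. This stands. The case for adjustment rests on recovering precision and on reading a single trial, not on invalidity.

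**Route is not reserve.** Route 1 also admits women with low reserve, and route 2 can be met on AMH alone with a count above 5. This stands too, and is why the adjustment should use measured AFC or the reserve test and not the entry route.

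**One comparison is immune.** The protocol also compares native with reimplanted ovary within each patient, which imbalance between arms cannot distort. True, but the between-arm comparison is the randomised one and is unprotected.

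**A stronger reading.** A reader might infer that the protocol expects different or even opposite results in the two kinds of women, so that a null pooled result could mean only that the wrong women were enrolled. The background does mention "a group of young women with low ovarian response have normal basal FSH hormone levels in whom there is no apparent cause" for their response, and offers "a decrease in the number of FSH receptors available in the granulosa cells, FSH post-receptor defects, etc" among its hypotheses. But it calls these hypotheses unproven, ties them to neither a normal AFC nor route 1, and they bear on response to gonadotrophins, a secondary objective. Sections 1 and 2 predict a rise in antral follicles without distinction by reserve. In the earlier series in section 1, all eight responders were among the 13 women with residual follicles (8/13 = 62%, as stated), which if anything suggests that better reserve helps. At most, the size of the effect may differ by reserve.

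**Conclusion.** The point holds as a loss of precision and of interpretability. Two kinds of women can enter, a likely strong predictor of the main outcome is measured before treatment, and neither allocation nor analysis uses it. On the stated assumptions, a 20-point imbalance in normal-reserve share arises in 16 to 20% of trials with a 30/30 split (10 to 15.5% with simple allocation), and power falls from 80% to about 65 to 70% at a 4-follicle gap. The normal-reserve share, the gap and the SD are all assumed; at a 2-follicle gap the loss is only 3 to 4 points.

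The documents do not support a claim of bias, of inflated type I error or of opposite expectations in the two groups. Nor would adjustment rescue power if the effect really differed by reserve: with no effect in half the women and D = 4, simulated power is 24% unadjusted and 27% adjusted.

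**What to change.** Make the main between-arm comparison of AFC a linear model (ANCOVA) with arm and baseline AFC, the baseline taken on the same per-ovary or total basis as the outcome. At the least, adjust for whether the reserve test at randomisation was abnormal or normal. Baseline AFC is preferable because it keeps information that two strata discard.

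Report AFC, AMH and entry route at baseline by arm. Arm differences within reserve strata, with confidence intervals, can be given as exploratory; 60 women are too few to settle whether the effect differs.

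The SAP describes allocation in the past tense. Separate envelope series by reserve stratum apply only if allocation is not finished; the adjusted analysis works either way.

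The cost is one line of SAP text and one extra model, with no new measurements. If the adjusted model is added after outcome data have been seen, the report should say so and show the unadjusted result beside it.

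### The day 2-5 rule for antral follicle counts cannot cover all the fortnightly follow-up scans, and the SAP neither names the count to be tested nor uses baseline AFC

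*Protocol*

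**What the plan says.** AFC carries the main objective (Protocol, section 3). Four parts of the plan bear on how it is measured and compared.

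- **Timing rule.** Protocol section 5, under the assessment of ovarian reserve: "Antral follicles were counted on day 2-5 of the menstrual cycle". The sentence has no qualifier and shares a bullet with the description of the scanner.
- **Schedule.** Protocol section 4, Phase 1 variables, lists "Antral follicle count at randomisation (per ovary") and then "Antral follicle count after intervention/control (per ovary, fortnightly for 6 months"). The design text agrees: "Subsequently, bi-weekly ultrasound monitoring was performed". No cycle-day window is given for follow-up, and no event is named that starts the fortnightly clock in either arm.
- **Population.** The exclusion for anovulation relies on "irregular cycles and serum progesterone on day 21 of the cycle", so the trial expects women whose cycles reach day 21. Cycle length is not stated.
- **Comparison.** Protocol section 4: "The number of antral follicles in both intervention groups was compared". The SAP's only sentence on such outcomes begins "Comparison of quantitative variables was performed using the" and goes on to name Student's t-test or the Mann-Whitney test. It mentions no visit, per-woman summary, repeated-measures method, baseline adjustment or cycle day.

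**The concern.** A scan every 14 days and a four-day window once per cycle cannot both be met at every visit in a cycling woman. A reader therefore cannot tell which counts followed the rule. If the rule governs only the baseline count, a change from baseline may combine cycle timing with treatment and time.

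The second gap would remain even if timing were settled. A two-group test needs one value per woman. The plan produces about 13 and does not say which of them, or what summary, is tested. It also measures baseline AFC and then does not use it. At stake are the clarity of the main result and precision in a trial of only 60 women.

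**Working it through.** The plan gives no scan count, power or precision figure, so there is nothing to reproduce first.

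**1. Number of follow-up scans.** Six months taken as 182 days: 182/14 = 13. Taken as 24 weeks: 168/14 = 12.

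**2. How many can fall on day 2-5.** The window spans 3 days from first to last. Two scans in the windows of successive cycles are at least L - 3 days apart, where L is the cycle length. A spacing of 14 days satisfies this only if L - 3 ≤ 14, that is L ≤ 17. For L ≥ 18, two consecutive scans cannot both qualify, so at most every second scan does:

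- free start: at most ceil(13/2) = 7 of 13, so at least 6 outside (6 of 12 on the shorter count);
- clock starting from an in-window baseline scan: scan 1 must miss, so at most 6 of 13 qualify and at least 7 (54%) are outside.

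Among constant cycles of 21 to 35 days, 7 is reached only at exactly 28 days with favourable alignment. The other lengths give a maximum of 2 to 5.

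**3. Visit tolerance (assumption).** If visits may move by w days, the largest spacing is 14 + 2w and the bound needs L ≥ 18 + 2w: 20, 22 or 24 days for w = 1, 2 or 3. With cycles of 18-23 days and w = 3, the minimum outside falls to 3-5 of 13.

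**4. Typical rather than best case (assumption).** For scans not timed to a 28-day cycle, the expected number in the window is 13 × 4/28 = 1.9, so about 11 of 13 are outside. In a simulation with mean cycle 28 days, SD 1/2/3 days and an in-window baseline, 70/80/84% of scans are outside with exact visits. With visits moved by up to 3 days into the window whenever possible, it is 55/61/64%. Women with no in-window follow-up scan are 8/15/15% and under 0.3% respectively.

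**5. Precision from using all counts and baseline (assumption: equal variance, set to 1, and equal correlation r between all counts including baseline; effect constant over time).**

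- One scan, unadjusted: variance 1.
- One scan, baseline-adjusted: 1 - r².
- Mean of 13 scans, unadjusted: r + (1 - r)/13.
- Mean of 13 scans, baseline-adjusted: r + (1 - r)/13 - r².

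For r = 0.5 the last is 0.5 + 0.038 - 0.25 = 0.288, and its square root is 0.54.

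| r | Adjusted mean, variance | SE vs one unadjusted scan | SE vs unadjusted 13-scan mean | One scan, adjusted vs unadjusted: √(1 - r²) |
|---|---|---|---|---|
| 0.3 | 0.264 | 0.51 | 0.86 | 0.95 |
| 0.5 | 0.288 | 0.54 | 0.73 | 0.87 |
| 0.7 | 0.233 | 0.48 | 0.57 | 0.71 |
| 0.9 | 0.098 | 0.31 | 0.33 | 0.44 |

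**6. If the effect is late.** Suppose there is no effect at the first 8 of 13 scans and a full effect at the last 5. The all-scan mean then carries 5/13 = 0.385 of the effect. Relative to one unadjusted late scan, the z ratio is 0.385/0.51 = 0.75, 0.385/0.54 = 0.72 and 0.385/0.48 = 0.80 for r = 0.3, 0.5 and 0.7. The average can therefore lose to a well-chosen late visit.

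**The case against.** The strongest reply is that there is no contradiction. The day 2-5 sentence stands under the assessment of ovarian reserve, and section 4 has women "randomised to two treatment arms after assessment of ovarian reserve", while follow-up scanning goes by another name, monitoring. A baseline-only reading is natural and removes the conflict. This stands as a reading, but no text states it. The same bullet describes the scanner, which presumably served every scan. On that reading at least 6 of 13 follow-up counts are still outside the baseline window.

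Four stronger conclusions that a reader might draw are not supported:

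- *Most follow-up counts are off-window.* The unconditional minimum, 6 of 13, is not a majority. A majority needs an assumed clock start or assumed cycle lengths.
- *Those counts are in another cycle phase.* A count on day 6-8 misses the window but may still be follicular. The figures count missed windows, not changes of phase.
- *The main comparison is biased.* The documents give no variation of AFC by cycle day. If both arms are scanned on the same clock, randomisation balances cycle timing in expectation and what remains is noise. Different timing by arm is possible, since one arm has surgery and the other no intervention, but it is not documented. The native versus reimplanted comparison is less exposed when both sites are counted at the same scan.
- *The SAP's tests are invalid.* A t-test or Mann-Whitney test on one named visit or a per-woman mean would be valid. What is missing is the named quantity and the baseline adjustment.

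It is also fair to say that cycle day is observed after randomisation, and after unilateral oophorectomy in one arm, so it does not belong in the main model. An all-scan average can also dilute a delayed effect, which the protocol's mechanism (primordial follicles growing into antral ones) makes plausible. The fix allows for both.

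**Conclusion.** The point holds in two separate parts.

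First, the timing rule and the follow-up schedule are not reconciled. The bound rests on exact 14-day visits and cycles of at least 18 days; tolerance or shorter cycles loosen it as shown. This is a gap in clarity, and an effect on bias or power has not been demonstrated.

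Second, the SAP leaves the main outcome to an unadjusted two-group test on an unspecified value. Baseline adjustment with averaging would bring the standard error to 31-54% of that of one unadjusted scan; baseline adjustment alone at a single scan brings it to 44-95%. Both ranges assume equal correlation of 0.3-0.9, and the first also assumes an effect constant over time. Neither owes anything to a cycle-day term. The change should be made, with medium confidence in its practical size, because the documents give neither the correlation between counts nor their within-cycle variation.

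**What to change.** 1. **Reconcile the protocol.** State whether day 2-5 applies to follow-up counts or to baseline only. Start the fortnightly clock from the same event in both arms, for example randomisation; if scanning is complete, report what was done in each arm.
2. **Main analysis.** In the SAP, compare arms on all follow-up counts in all randomised women, adjusted for baseline AFC and without cycle day. Use ANCOVA on the per-woman mean, or a repeated-measures model with a random effect per woman. Name one AFC measure, total or per ovary. Include visit and treatment-by-visit terms and report results by visit, so that a late effect can be seen. If Phase 2 stimulation or pregnancy falls within the six months, say how those counts are handled.
3. **Sensitivity analyses.** Where menses dates exist, add a cycle-day-adjusted model and an analysis restricted to day 2-5 scans. Where they do not, state cycle timing as a limitation.
4. **Labelling.** If results are already known, call the analysis post hoc.

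The cost is a clarifying sentence or two in the protocol, SAP wording and slightly more analysis. No scan or treatment changes, and the main model needs no menses dates. The remaining downside is dilution of a late effect in the overall average, which is why the by-visit results are required.
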